6.4.1.6. Measurements

- 1) FVC (liters and percent predicated for FVC) (Hankinson, 1999)
- 2) FEV₁ (liters per second and percent of predicted for FEV₁) (Hankinson, 1999)
- 3) Exhaled carbon monoxide as an indicator of recent smoking
- 4) IC
- 5) Bronchodilator reversibility of FEV₁ and FVC
- 6) FEV₁/FVC
- 7) Six-minute walk distance
- 8) Area above the oxygen saturation-time curve during the six-minute walk

6.4.1.7. Human Subjects' Protection and Risks

PFTs are a common medical procedure of generally low risk. Some participants may experience breathlessness, cough, fatigue, dizziness/lightheadedness (hyperventilation), all of which are brief, and very rarely headache, syncope, musculoskeletal chest pain, rib fractures, or ear injury. An episode of stress incontinence (urine leakage) may be caused by the PFT maneuvers in susceptible individuals. A seated position has been specified to reduce risk related to dizziness or syncope. Transmission of airborne disease is rare and minimized or eliminated with single-use filters.

Instructions for withholding bronchodilator medications prior to testing will stress the continued use of rescue medication if needed. The use of albuterol or ipratropium will generally relieve any symptoms related to the trough effect of long-acting bronchodilators.

Albuterol has been reported to cause urticaria, angioedema, paradoxical bronchospasm, angina, arrhythmias, QT prolongation, hypertension, hypokalemia, seizures, tremor, nervousness, headache, tachycardia, muscle cramps, palpitations, insomnia, and dizziness.

Ipratropium has been reported to cause cough, nausea, dry mouth, dizziness, headache, dyspnea, atrial fibrillation, tachycardia, paradoxical bronchospasm, laryngospasm, angioedema, anaphylaxis, hypersensitivity, and exacerbate narrow-angle closure glaucoma.

The dose used in testing is twice the usual dose of albuterol (one dose every four hours) or ipratropium (one dose every six hours) used chronically. However, home management of exacerbations includes increasing the dose and/or frequency of bronchodilator therapy (GOLD, 2007). Doses in patients hospitalized or visiting the Emergency Department for exacerbations may be ten times the usual dose. Repeat dosing after at least three hours, is unlikely to result in any additional side effects, if necessary for the scheduling of the plethysmography.

The six-minute walk test is self-paced, but participants are encouraged to cover as much distance as they can in six-minutes. As with any walk, the participant may stumble or fall. It is expected that more severe participants will become short of breath and may need to stop to recover before six minutes have elapsed. The walk test will be stopped if the participant's S_pO_2 falls below 80%.

Data transmission will be encrypted with a 128-bit VPN approach. The PFT software is designed to be HIPPA compliant for clinical use.

The participant may benefit from treatment or secondary prevention after study identification of unrecognized pulmonary disease. All study personnel are certified in the ethical conduct of human biomedical and genetics research and HIPPA information security.

6.4.2. Anthropometric Measurements

6.4.2.1. Background and rationale

Anthropometric measurements are an easy, cost-efficient method for calculating body composition. Numerous studies have shown that these measurements are predictive of health outcomes, including risk of cardiovascular disease and obstructive sleep apnea.

In patients with COPD, low body mass index (BMI) is independently predictive of all cause mortality (Landbo, et al, 1999). Conversely, high BMI negatively impacts exercise performance in the setting of COPD (Schols, et al, 1991). In addition, in a study by Chen, et al (2007), waist circumference was negatively associated with pulmonary function after adjusting for sex, age, height, weight, and pack-years of smoking.

6.4.2.2. Inclusion/exclusion specific to procedure

6.4.2.2.1. Inclusion criteria

There are no additional inclusion criteria.

6.4.2.2.2. Exclusion criteria

Participants must be able to stand and straighten spine.

6.4.2.3. Methods

6.4.2.3.1. Standing Height

Standing height will be assessed using a mounted stadiometer. The study coordinator will record the measurement to the nearest tenth of a centimeter.

6.4.2.3.2. Arm span

Arm span will be measured using a study-provided measuring tape. The participant will stand with his or her back against a wall. With his or her arms held level with his or her shoulders as widely as possible, the study coordinator will measure the distance from finger tip to finger tip.

6.4.2.3.3. Waist

To define the level at which the waist or abdominal circumference is measured, you must first locate and mark a bony landmark, the lateral border of the ilium (i.e., top of the hip). The recorder (if available) makes sure that the tape is parallel to the floor and that the tape is snug, without compressing the skin. Measurements are made at the end of a normal expiration and reported to the recorder to the nearest centimeter.

6.4.2.3.4. Hip

The hip girth is measured at the level of maximal protrusion of the gluteal muscles (hips).

6.4.2.3.5. Neck

Neck measurements should be taken between the midcervical spine and midanterior neck using a study-provided plastic measuring tape.

6.4.2.3.6. Weight

Participants will be asked to self-report weight prior to being weighed. Participants' weight will be measured using a digital scale. Study coordinators will record the digital weight readout (tenth of a kg).

6.4.2.4. Measurements:

1. Height
2. Arm Span
3. Waist Circumference

4. Hip Circumference
5. Neck Circumference
6. Weight
7. Body Mass Index (BMI)
8. BODE (calculated in part using BMI)

6.4.2.5. Human Subjects' Protection and Risks

There is a low probability of participants' experiencing an adverse or unanticipated event during anthropometric measurements. Clinical risks include syncope and vasovagal episodes. Participants may also experience feelings of embarrassment or discomfort with being measured. Efforts to minimize these risks include conducting the measurements in a quiet, private location. Study coordinators should approach participants in an open, tolerant manner, reassuring them during the procedures that they can stop at any time. Further, coordinators should carefully describe the measuring process before initiating it so that the participant is not surprised at any step.

6.4.3. Blood Pressure

6.4.3.1. Background and rationale

High blood pressure is a known risk factor for many diseases, including cardiovascular disease, stroke, and kidney failure. SPIROMICS will use the following cut points for determining the presence of hypertension (NHLBI, 2004):

Table 5. Blood Pressure Cutoffs

Category	Systolic		Diastolic
Normal	<120 mmHg	And	<80mmHg
Prehypertension	120-139mmHg	Or	80-89mmHg
HBP Stage 1	140-159mmHg	Or	90-99mmHg
HBP Stage 2	>160mmHg	Or	>100mmHg

6.4.3.2. Inclusion/exclusion specific to procedure

6.4.3.2.1. Inclusion criteria

There are no procedure specific inclusion criteria.

6.4.3.2.2. Exclusion criteria

Any condition that prevents the study coordinator from placing the blood pressure cuff on either of the participants' arms (e.g., amputation, rashes, small gauze/adhesive dressings, casts, arm withered, puffy, have tubes, open sores, hematomas, wounds, arteriovenous (AV) shunt, or any other intravenous access device) are exclusion criteria..

6.4.3.3. Methods

1. Blood pressure (BP) will be measured using an automated device. Coordinators should measure the participant's arm to determine appropriate cuff size.
2. BP will be taken from the right arm unless some condition (such as noted in the exclusion criteria) prevents use of that arm. Coordinators may use the left arm in this situation.
3. Participants will be asked to sit quietly with their feet on the floor and with their arm resting in their lap. Cuff will be placed on the arm and the automated BP device activated. Coordinators will take three consecutive measurements with 30 second intervals between each measurement.

6.4.3.4. Measurements:

1. Systolic BP
2. Diastolic BP
3. Pulse

6.4.3.5. Human Subjects' Protection and Risks

There are no significant risks associated with measuring blood pressure. Participants may experience discomfort in the form of mild pressure, tingling, or numbness while the BP cuff is active.

6.4.4. Multidetector-Row Computed Tomography (MDCT)

6.4.4.1. Background and Rationale

The Radiology Center for SPIROMICS will oversee the acquisition of a state-of-the-art computed tomography (CT) image data set acquired for the purpose of providing lung phenotypes associated with COPD. Data will be acquired appropriately, transmitted securely, assessed for quality and protocol adherence, archived safely with quantitative image analysis results, and results will be transmitted appropriately.

Multidetector-row computed tomography (MDCT) provides the ability to image the lung with a theoretical in vivo resolution of approximately 0.5mm. The whole lung can be imaged at this resolution in approximately 10 seconds, well within a single breath hold. Scanner rotation speeds are on the order of 300 ms per revolution. With advances in image processing methods, the lung, lobes, bronchial tree, and vascular trees can be extracted and quantitatively assessed. Density and texture measures of the lung parenchyma via MDCT imaging are now providing tools for establishing regional presence and distribution of lung pathology including emphysema-like lung tissue found at full inspiration and air trapping found at full expiration.

6.4.4.2. Inclusion/exclusion specific to procedure

All participants meeting primary inclusion and exclusion criteria for entrance into the SPIROMICS study will have a CT scan.

6.4.4.3. Methods

Prior to participant enrollment CT scanners at each site will be calibrated using the COPD Gene Lung Phantom (CTP674, The Phantom Lab). Please see Section 8.5.3 for details on the CT quality assurance plan.

Although there are some variations between CT scanners, a standardization of the parameters has been developed to allow multiple scanners to output reliable quantitative measures across a given patient population. Please see the Imaging MOP for details. Upon arriving at the CT site the study coordinator will check with the radiology technician to insure that appropriate study protocol is followed. Study coordinators are provided with a cheat sheet (see Imaging MOP) to assist in confirming the appropriate CT scanner settings. BMI will be used to determine large (BMI >30), medium (BMI 20 to 30), or small (BMI <20) mAs setting. The BMI values will be provided to the radiology technician by the study coordinator.

All participants will be imaged in the supine body posture. Scout scans will be obtained to minimize the subject's exposure to radiation and must be performed at the lung volume for which anatomical boundaries are being evaluated. Each study site should perform scouts as deemed locally appropriate to specify a TLC and RV scan such that when spirally scanned, the full extent of the lung is acquired at the respective lung volumes and over-scanning is kept to a minimum (no more than 2 cm cephalad to the apical or 5 cm caudal to the basal lung borders). Inadequate scout scans may be repeated as per site-specific determination. (Spiral scans, however, may not be repeated.) The exposure factors (kV and mA) for the topogram should be set to the lowest available on the CT scanner that provides an acceptable image. For GE scanners 80 kv and 20 mA is sufficient to achieve satisfactory scout image quality. Two CT scans will be performed each at different lung volume. The first volume will be at Total Lung Capacity (TLC) followed by another CT scan at Residual Volume (RV). Study coordinators will be provided with a script to coach participants in the appropriate breathing technique (See Imaging MOP).

CT scans should be conducted after the participant has received the bronchodilator dose administered for post-bronchodilator spirometry. For CT scans occurring on the same day as spirometry, if the scan occurs more than 165 minutes after the last dose of bronchodilation, then the participant will need to be re-dosed as described in Section 6.4.1.4 and Table 4.

If the CT scan occurs on a separate day from spirometry, subjects should not withhold bronchodilators prior to the study visit for the CT scan. Subjects will receive 2 puffs of albuterol and 2 puffs of ipratropium before the CT scan as described in Section 6.4.1.4.

At all visits subsequent to the baseline visit, participants will be scanned at the same dose as was used during the baseline CT visit unless either 1) the original scan was at a higher than appropriate dose (e.g., small subject scanned as a medium) or 2) the participant's BMI has changed more than three units on either side of the BMI thresholds for dose categories.

6.4.4.4. Measurements

1) Primary candidate outcomes / phenotype measures:

- Volume measures (assessed for whole lung, left and right lung and lung lobes):
- Total volume at TLC and RV
- Total air volume at TLC and RV
- Total tissue (non-air) volume at TLC and RV

Primary parenchymal measures to be assessed from the TLC scans on a per lung, right and left lung, and lobar basis in this study are:

- Lower 15th percentile point (in Hounsfield Units: HU) of the lung density histogram assessed from TLC scans at baseline and the rate of leftward shift over time.
- Percent of voxels below -950, -910, 850, and their change over time.
- “Alpha” assessed for holes defined as connected voxels whose values fall below -950 HU.

Primary parenchymal measure to be assessed from the RV scans on a per lung, right and left lung and lobar basis in this study are:

- Percent of lung voxels below -850. (index of air trapping) and its change over time.

Primary airway measures to be assessed at each airway segment out to 6 generations (as detectable) along 6 paths (RB1, RB4, RB10, LB1, LB4, and LB10)

- Luminal area at baseline and over time
- Luminal perimeter at baseline and over time
- Average wall thickness at baseline and over time
- Wall area percent at baseline and over time

2) Secondary outcomes / phenotype measures:

These measures are less well tested in the literature and will be performed in an attempt to evaluate their utility in the identification of COPD phenotypes and disease progression.

Secondary parenchymal measures to be assessed from the TLC scans:

- Parenchymal measures assessed for sub-lobar (areas of influence of primary lobar airways) segments including change over time
- Raw texture measures on a lobar and sub-lobar basis including change over time

Secondary parenchymal measures to be assessed from the RV scans:

- Percent of voxels falling below -850 evaluated for sub-lobar segments and the change over time
- Pulmonary artery vascular volume assessed for the arterial volume within the borders of the lung out to the 5th generation pulmonary arteries and the change over time

6.4.4.5. Human Subjects' Protection and Risks

There is a low probability of serious risks in these radiological studies. There is a theoretical risk from radiation exposure from the CT scans, but the doses of radiation are within acceptable exposure limits. This is not a therapeutic intervention study, and will not compromise standard, usual care.

The x-ray exposure during these studies will be limited to roughly the area covered by the rib cage. Although there are no proven harmful effects from the radiation received during this study, long-term effects of this radiation on participants' health cannot be excluded with certainty. The total radiation received over the course of the study will be equivalent to less than the annual radiation limit for a medical radiation worker.

These scanning images are not intended as a replacement for a physical examination or a substitute for a visit to the participant's doctor; nevertheless, they will be reviewed by a local radiologist. If there are any abnormalities observed by the clinical center radiologists these will be reported to the clinical site Principal Investigator. Furthermore, the Radiology Reading Center personnel will report abnormal results found during the central read to the GIC. The GIC will in turn direct those results to the appropriate clinical center.

The risks of the abnormal findings are:

- False positive scan, which is an abnormality that initially is of concern for cancer that is later found not to be cancer. Anxiety may result from false positive results.
- Detection of abnormalities unrelated to lung cancer that could lead to unnecessary testing or treatment
- Failure to detect a lung cancer that is present, and possibly miss an opportunity for care

6.4.5. Biospecimen Collection

6.4.5.1. Background and rationale

For large pharmaceutical trials, biomarkers for patient subgrouping or as measures of intermediate outcomes will optimally be obtained in samples that are patient-friendly and non-invasive, such as blood and urine.

6.4.5.2. Inclusion/exclusion specific to procedure

All participants meeting primary inclusion and exclusion criteria for entrance into the SPIROMICS study will have samples drawn for blood and urine at baseline, Year 1, and Year 3.

6.4.5.3. Methods

6.4.5.3.1. Collection of Blood:

In an effort to reduce experimental variability, venous blood samples should be drawn from participants in the morning after a fast initiated at midnight. The following blood samples should be collected, limited to no more than eight tubes of blood drawn per day/visit. The recommended order of the blood draw is as follows:

- 2 tubes of blood allowed to clot for serum, which will be processed within 2 hours of collection as described in the Biospecimen Collection and Processing Manual of Procedures, MOP 4, for future batch shipment on dry ice to the GIC.
- 1 tube of plasma collected in a P100 tube for preservation of plasma proteins in anticipation of proteomics analyses. Plasma should be processed within 2 hours of collection as described in MOP 4 for future batch shipments on dry ice to the GIC.
- 1 tube of plasma collected in EDTA for submission directly to the local clinical laboratories for complete blood count with white blood cell differential and platelet count.
- Three tubes of blood collected in EDTA for plasma and DNA which will be processed within 2 hours of collection as described in MOP 4 for future batch shipment to the GIC. After the baseline visit, only the plasma will be collected from these tubes unless a participant's DNA sample is lost or damaged, in which case processing for DNA will occur during the Year 1 clinic visit.
- 1 tube of blood in PAX-Gene™ RNA tube. This tube will be shipped to the GIC laboratories for RNA extraction (including preservation of micro RNA species). RNA will be suitable for all down-stream applications (transcriptomics, RT-PCR).
- 1 tube of plasma collected in citrate to be processed for plasma and buffy coat cells within two hours for future batch shipments on dry ice to the GIC.

The above collections total approximately 70 ml per visit

- 1 additional tube may be collected if the following analysis is needed.
 - Some sites may require blood pregnancy test before MDCT, which is conducted on a sample of serum (red-top or serum gel tubes). This would only be required when urine pregnancy test is not acceptable at the site and for women of child-bearing age.
- Sites may redraw blood tubes up to two of the blood tubes if needed because of problems in specimen processing.

6.4.5.3.2. Blood sample processing:

The goal is to obtain an adequate number of very high quality aliquots to support all analyses within SPIROMICS and future ancillary studies. Quality assurance guidelines are outlined in the MOP 4. Briefly, plasma and serum tubes should be processed within 2 hours after collection according to the methods outlined in MOP 4. Aliquots range in volume from 100-500 µl. All

samples should be stored and batch shipped according to procedures outlined in MOP 4. As a general rule, buffy coat cells collected from the plasma tubes should be frozen for shipment to the GIC to serve as an alternative source of DNA if such a sample is needed.

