6.2. Schedule of Measurements

Table 3. Schedule of Study Measurements

	V1	V2	V3	V4
Physiological Measures				
Pulmonary Function Testing				
Exhaled CO (eCO)	X	X		X
Forced Vital Capacity	X	X	X	X
Slow vital capacity	X	X	X	X
Bronchodilation	X	X	X	X
Forced Vital Capacity	X	X	X	X
Slow Vital Capacity	X	X	X	X
Six minute walk test with continuous pulse oximetry	X	X	X	X
Anthropometric Measurements				
Height	X	X	X	X
Weight	X	X	X	X
Arm Span	X	X	X	X
Waist	X	X	X	X
Hip	X	X	X	X
Neck	X	X	X	X
Seated Blood Pressure	X	X	X	X
MDCT	X	X		
Biospecimen collection				
Blood				
Serum (Two - RT)	X	X		X
Plasma (One - P100)	X	X		X
Plasma (Three - Plasma/DNA w/EDTA and One CBC w/EDTA)	X	X		X
Plasma (One –with citrate)	X	X		X
RNA (One – PAX - Gene)	X	X		
Urine	X	X		X
Induced Sputum	X	X*	X*	X*
Questionnaires				
Medical History	X	X	X	X
St. George’s Respiratory Questionnaire	X	X	X	X
MOT Short Form – 12	X	X	X	X
COPD Assessment Test	X	X	X	X
Modified Medical Research Council (MRC) Dyspnea Scale	X	X	X	X
Sleep questionnaires				
Berlin Questionnaire	X	X	X	X
Pittsburgh Sleep Quality Index	X	X	X	X
Veterans Specific Activity Questionnaire	X	X	X	X
Hospital Anxiety and Depression Scale (HADS)	X	X	X	X
FACIT	X	X	X	X
Questionnaire for Ease of Cough and Sputum Clearance	X	X	X	X

*Sample collection attempted only if initial collection at baseline failed.

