9.2.2.6.2. Blinded Replicate

A replicate sample is obtained by either drawing one to two additional tubes of blood or by dividing a urine sample into separate containers. The replicate samples are then processed using the same method as for the original samples. Investigators and laboratory staff analyzing and processing the samples should be unable to distinguish original samples from replicate samples. Over the entire study, replicate samples will be obtained on 5% of each specimen type (n = 160 at baseline, n=151 at year 1, and n=134 at year 3 for each specimen). Nine participants will be needed to provide a complete set of 9 QC replicate specimens (8 tubes of blood and 1 urine specimen), unless urine is collected from a participant providing a blood specimen replicate. In general only one additional tube of blood will be taken for a replicate sample from a participant. If a site needs to “catch up” to ensure a 5% sample of each replicate is obtained, up to two replicate samples blood can be drawn from one participant, while remaining under the 7 tablespoon limit. At baseline and year 1 just under half of the participants (45%) will contribute to the pool of replicate samples. In year 3 approximately 40% of participants will contribute to the replicate samples.

Details on the implementation of the replicate study and data analysis are available in MOP 7 – Quality Assurance and Quality Control.

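### The blood collection section caps the draw at eight tubes per day/visit but lists nine tubes under that cap, and the replicate section uses a different limit in a different unit

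*Protocol*

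**What the plan says.** Section 6.4.5.3.1 (Collection of Blood) introduces its list of samples with the condition that collection is "limited to no more than eight tubes of blood drawn per day/visit". The list then gives:

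- "2 tubes of blood allowed to clot for serum"
- "1 tube of plasma collected in a P100 tube"
- "1 tube of plasma collected in EDTA for submission directly to the local clinical laboratories"
- "Three tubes of blood collected in EDTA for plasma and DNA"
- one PAX-Gene tube for RNA
- one citrate tube

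The section puts the total at about 70 ml per visit. It then allows one further tube where a site needs a blood pregnancy test, and a redraw of up to two tubes after processing problems.

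Table 3 (section 6.2) repeats the set, with the EDTA tubes on one line as "Plasma (Three - Plasma/DNA w/EDTA and One CBC w/EDTA)". The RNA tube is marked at V1 and V2 only. All other blood tubes are marked at V1, V2 and V4.

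Section 9.2.2.6.2 (Blinded Replicate) describes a full replicate set of eight blood tubes and one urine specimen. It says: "In general only one additional tube of blood will be taken for a replicate sample from a participant". A site that has fallen behind may draw two, "while remaining under the 7 tablespoon limit".

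Section 6.3 lets the procedures of one visit be spread over several days within 42 days.

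**The concern.** A limit on how much blood is taken from a participant is an operating rule that sites and ethics boards will hold the study to. Here the limit and the collection it governs stand in the same section and disagree. A coordinator who draws everything on the list in one sitting exceeds the stated cap. One who stops at eight tubes leaves a scheduled specimen uncollected.

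The protocol names no specimen to give up first, so sites could settle the conflict in different ways. Missing specimens could then differ by site for an administrative reason. Baseline and Year 1, the two visits affected, supply the one-year changes that section 7.4.3 uses as candidate intermediate outcomes. The second limit, in tablespoons, adds to the uncertainty because the protocol does not say how it relates to the tube cap.

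**Working it through.** **Count of the list in section 6.4.5.3.1.** 2 serum + 1 P100 + 1 EDTA for blood count + 3 EDTA for plasma/DNA + 1 PAX-Gene + 1 citrate = 9. The cap is 8, so the excess is 9 − 8 = 1. The three EDTA plasma/DNA tubes are still drawn after baseline; only the DNA processing stops.

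**Count by visit from Table 3, against the cap of 8:**

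| Visit | Tubes scheduled | Tubes without the blood-count tube |
|---|---|---|
| Baseline (V1) | 9 | 8 |
| Year 1 (V2) | 9 | 8 |
| Year 3 (V4, no RNA) | 8 | 7 |

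The stated figure of eight is reproduced at Year 3, or at baseline and Year 1 if the locally sent blood-count tube is left out. It is not reproduced for the full list at baseline or Year 1.

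**Check against the replicate section.** Eight blood tubes plus one urine specimen is nine specimens; 9 × 5% = 45%, which is the share of participants that section 9.2.2.6.2 expects to contribute at baseline and Year 1. Without the RNA tube, eight specimens × 5% = 40%, its Year 3 figure. So that section counts eight blood tubes in a full set, which is the nine listed tubes less the blood-count tube.

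**Number of participants affected if the cap is per visit.** At baseline, all 3,200 planned participants. At Year 1, the 151 replicates per specimen represent 5%, so about 151 / 0.05 = 3,020 attend. Each would be one tube over.

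**Effect of the permitted extras at baseline or Year 1, if they count toward the cap.** One pregnancy tube: 9 + 1 = 10. One or two replicates: 10 or 11. Two redraws: 11.

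**The two limits compared.** Assume equal tube volumes and 14.8 ml per tablespoon; the protocol gives neither. Then 70 / 9 ≈ 7.8 ml per tube, and seven tablespoons is 7 × 14.8 ≈ 104 ml. The routine nine tubes plus two replicates come to 11 × 7.8 ≈ 86 ml. That draw is inside the tablespoon limit but, if replicates count, three tubes over the tube cap.

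**The case against.** Three arguments on the other side have weight.

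First, the cap is worded per day/visit, and section 6.3 lets a visit run over several days. Read per day, nine tubes can be drawn without a breach. This stands, so it is not correct that the cap can never be met. But it would need a split draw from every participant at baseline and Year 1. Section 6.4.5.3.1 describes a fasting morning sample and a per-visit total, and mentions no split.

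Second, the cap may have been counted without the blood-count tube, since the replicate section arrives at eight that way. This is a plausible origin of the mismatch. The text does not say so, however: the cap covers tubes drawn, the blood-count tube is in the list beneath it, and nothing exempts it.

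Third, the pregnancy, redraw and replicate tubes are expressly authorised, and can be read as additions to the general cap. This also stands. A reader might infer that sites cannot draw replicates at all, or that Year 3 leaves no room for one. The documents do not support that, because section 9.2.2.6.2 instructs sites to draw them.

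A reader might also add every permission together (9 + 1 + 2 + 2 = 14 tubes, about 109 ml) and call that the permitted maximum. It is not: the second replicate is allowed only under the tablespoon limit, about 104 ml on the same assumptions. Nor does it follow that citrate plasma, last in the list, would be lost. The draw order is only recommended, and Table 3 schedules that tube at all three blood visits.

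**Conclusion.** The protocol contradicts itself by one tube. Nine tubes are listed and scheduled at baseline and Year 1 under a cap of eight. Read per visit, every participant's routine draw at those two visits exceeds the cap; read per day, compliance depends on a split draw that the protocol does not describe. The routine Year 3 draw meets the cap exactly.

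The protocol also leaves open which tubes count, and it states a second limit in another unit. The count needs no assumption beyond the two lists; only the millilitre comparison rests on equal tube volumes and the size of a tablespoon.

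The defect is operational. It changes no power calculation or error rate. Site-dependent specimen loss is a possibility, not something the documents show: the biospecimen manual (MOP 4), which is not available here, and central training may already guide sites. Neither would make the protocol's own cap and list agree.

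**What to change.** Reconcile section 6.4.5.3.1, Table 3 in section 6.2 and section 9.2.2.6.2:

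- State one participant limit in one unit, say whether it applies per day or per visit, and make it consistent with the tubes scheduled at each visit.
- Say whether the local blood-count tube and the pregnancy, redraw and replicate tubes count toward it.
- If the draw is meant to be split across days, describe that.
- Name the specimen to be omitted first when the limit is reached, so that any loss follows the same rule at every site.

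No particular limit and no order of omission is proposed here; both are for the investigators and the monitoring board. The cost is a wording change in those sections, with MOP 4 and the consent form checked for agreement. No new procedure is needed.
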